### **Occurrences of AEs and SAEs adjusted for exposure**

The exposure times by cohort is different, therefore, exposure adjusted occurrence rates will aid in the interpretation of differences in the occurrence of AEs/SAEs. Exposure adjusted occurrence rates will be presented (per 100 years of patient exposure), together with 95% confidence intervals. Summaries will be presented for treatment emergent AEs and SAEs.

Confidence intervals will be derived assuming a Poisson process for the occurrence of AEs (SAEs). See Section 5.4 for further details.

Summaries of exposure adjusted occurrence rates will be produced for AEs and SAEs by PT. Only AEs (SAEs) with more than 2 occurrences per preferred term will be displayed.

The analyses on occurrences of AEs and SAEs will be repeated by country.

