6.3 Treatments (pasireotide s.c., concomitant therapies)

The medication for this study is pasireotide s.c. Prescribing information on the pasireotide s.c. start and stop dates, dose, dose changes and reason for changes. The actual mean daily dose and duration of drug exposure while in the study will be summarized by descriptive statistics and corresponding listing will be presented. Incidence rates by person-time of exposure and incidence rates by person-time of observation with their corresponding 95% confidence interval will be reported.

Concomitant medications and significant non-drug therapies prior to and after enrolling into the study will be summarized by preferred term and ATC class of the WHO-Drug Reference List.

These analyses will be performed on the safety set.

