#### 6.2.4 Confidence intervals for occurrence rates of AEs and SAEs

The occurrences of AE or SAE by preferred term will be modeled to follow approximately a Poisson process with constant intensity  $\theta$ . The rate parameter  $\theta$  will be estimated as  $\lambda=D/T$ , where

- Numerator ( $D_i$ ) = total number of events (AE or SAEs by PT) observed within the cohorts and overall ( $i=1,2,3$  for cohort 1, 2 and overall, respectively). PTs which were reported more than once on the same day (within the same patient) will be counted as one event under the highest severity grade.
- Denominator ( $T_i$ ) = The sum of exposure time  $t$  across all patients in group  $i$  per 100 patient years. For a single patient the exposure time  $t$  is derived as:  $t = (\text{minimum date of (last dose + 28 days, last contact day, analysis cutoff day)} - \text{date of first dose during study} + 1) / 365.25$ . The sum of the exposure time of all patients in group  $i$  will be divided by 100 to obtain the exposure time per 100 patient years.
- Note: the analyses of safety and tolerability assessments will concentrate on the on-treatment period, defined to be the period from Day 1 to 28 days after last dose of pasireotide s.c. i.e. the exposure period for  $T_i$  is accordingly adjusted.

Conditionally on  $T$ , an exact  $100*(1-\alpha)\%$  confidence interval for a Poisson variable with parameter  $\theta*T$  and observed value  $D$  can be obtained based on (Garwood, 1936), from which an exact  $100*(1-\alpha)\%$  confidence interval for  $D/T$  will be derived as follows (Sahai, 1993; Ulm, 1990):

$$\text{Lower confidence limit } L = \frac{0.5c_{\alpha/2,2D}}{T} \quad (\text{in SAS: } (0.5*\text{cinv}(\alpha/2,2*D(i))/T(i))$$

$$\text{Upper confidence limit } U = \frac{0.5c_{1-\alpha/2,2D+2}}{T} \quad (\text{in SAS: } (0.5*\text{cinv}(1-\alpha/2, 2*D(i)+2)/T(i)) \text{ for } i=1,2,3 \text{ and } D(i) > 0 \text{ and } 0 \text{ otherwise,}$$

where  $c_{\alpha,k}$  is the  $\alpha$ th quantile of the Chi-square distribution with  $k$  degrees of freedom.

Garwood, F. 1936. Fiducial limits for the Poisson distribution. *Biometrika*. 28(3/4):437-442

Ulm, K. 1990. A simple method to calculate the confidence interval of a standardized mortality ratio. *American Journal of Epidemiology* 131(2):373-375.

Sahai, H. and Khurshid, A. (1993a). "Confidence intervals for the mean of a Poisson distribution: A review", *BiomtrcJ*, 35, 857-867.

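### For adverse events recorded once and then persisting, the SAP's only exposure-adjusted rate understates onset and depends on follow-up length; a first-event rate should stand beside it

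*SAP*

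**What the plan says.** SAP 6.2.4 defines the rate as D/T.

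- **Numerator D** is the "total number of events (AE or SAEs by PT) observed within the cohorts and overall". Only same-day repeats are merged: "PTs which were reported more than once on the same day (within the same patient) will be counted as one event". A repeat on a later day counts again.
- **Denominator T** runs, for each patient, from the "date of first dose during study" to the "minimum date of (last dose + 28 days, last contact day, analysis cutoff day", whichever comes first. Then "The sum of the exposure time of all patients in group $i$ will be divided by 100".
- **Model.** Occurrences "will be modeled to follow approximately a Poisson process with constant intensity", with exact (Garwood) limits.

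Nothing ends a patient's time at the first event, and nothing removes patients who already have the condition. SAP 8.4.1 applies this rate to all PTs with more than two occurrences. It gives the reason for doing so: "The exposure times by cohort is different, therefore, exposure adjusted occurrence rates will aid in the interpretation of differences in the occurrence of AEs/SAEs". No other exposure-adjusted figure is planned, and none is planned for the categories of adverse events of special interest (AESI).

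The AESI list in SAP 9.2 includes the PTs Type 2 diabetes mellitus, Cholelithiasis and Hypothyroidism.

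**The concern.** Events over total time is the right summary for something that can happen again, such as diarrhoea. A lasting condition is different. Protocol 3.5.2.1 has each adverse event followed until it resolves or is judged permanent, so such a condition will tend to be one record. Protocol 3.5.2.6 notes that HbA1c rose in the pivotal study and did not return to baseline. After onset the patient keeps adding time to T but cannot contribute another onset. The result is below the onset rate, and it still depends on exposure time, which is what it was brought in to adjust for.

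The cohorts add a second route. A prior user who already has the condition at entry cannot have a new onset on study, yet fills the Cohort 2 denominator.

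Long-term safety is the primary objective, and Protocol 1 gives long-term hyperglycaemia as one reason for the study. The affected terms are therefore among those that readers will look at first.

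**Working it through.** The documents state no adverse event rate, so there is no planned figure to reproduce. As a check on the limits, the SAP formula with D = 10 and T = 1 gives 4.80 to 18.39, as an exact Poisson interval should.

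**Inputs.** The rate, limits and time rule come from SAP 6.2.4. The 3-year plan per patient is in Protocol 3.1. Hazards of 2 to 40 per 100 patient-years (PY) and on-study times of 1 to 3 years are assumptions.

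**Step 1: expected rate.** Take a constant hazard h, one record per case and follow-up t for everyone. The SAP rate then has expectation (1 − exp(−ht))/t. With time ended at onset, the rate estimates h. For h = 0.20 and t = 3: (1 − exp(−0.6))/3 = 0.4512/3 = 0.1504, or 15.04 per 100 PY against 20. For t = 1 it is 18.13. The false cohort ratio at equal hazard is 18.13/15.04 = 1.21.

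| Hazard per 100 PY | SAP rate, 1 year | SAP rate, 3 years | Shortfall at 3 years | False ratio, 1 v 3 years | False ratio, 2 v 3 years |
|---|---|---|---|---|---|
| 2 | 1.98 | 1.94 | 2.9% | 1.02 | 1.01 |
| 5 | 4.88 | 4.64 | 7.1% | 1.05 | 1.03 |
| 10 | 9.52 | 8.64 | 13.6% | 1.10 | 1.05 |
| 20 | 18.13 | 15.04 | 24.8% | 1.21 | 1.10 |
| 40 | 32.97 | 23.29 | 41.8% | 1.42 | 1.18 |

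With 3 years in both cohorts and equal hazards the ratio is 1.00. If the hazards truly differ by a factor of 2, equal 3-year follow-up still shrinks the ratio to 1.94, 1.86, 1.74 or 1.55 for a lower hazard of 2, 5, 10 or 20.

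**Step 2: dropout.** A simulation used 100 patients, a 3-year cap, random discontinuation, hazard 20 and 4000 runs. At mean follow-up of 0.95, 1.90 and 2.59 years the SAP rate was 17.07, 15.74 and 15.29. The first-event rate was 20.01, 19.94 and 20.05.

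**Step 3: precision.** With 100 patients, 3 years and hazard 20, D = 45 and T = 3.00, so the SAP rate is 15.0 (10.9 to 20.1). Time ended at onset is 100 × 0.4512/0.20 = 225.6 PY, which gives 19.9 (14.5 to 26.7). At hazard 10, D = 26 gives 8.7 (5.7 to 12.7). Both SAP intervals still contain the assumed hazard.

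**Step 4: condition present at entry.** Suppose a share q of prior users already has the condition, cannot have it again and stays in T, and no one in Cohort 1 has it. With equal hazard and equal follow-up, the ratio of Cohort 1 to Cohort 2 becomes 1/(1 − q): 1.11, 1.25 and 1.43 for q = 10%, 20% and 30%.

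**Step 5: repeat records.** The extra records per case that would cancel the 3-year shortfall are h/rate − 1: 0.16, 0.33 and 0.72 at hazards 10, 20 and 40.

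**The case against.** **The quantity is honestly labelled.** The SAP calls it an occurrence rate and defines it openly. It is not a faulty estimator of something else. Worsening counts as treatment-emergent (SAP 8.4.1) and later repeats count in D, so a modest number of repeat records removes the shortfall. This stands, and it is why the point is limited to terms recorded once.

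**The cohort distortion is conditional.** A reader might infer that the longer-exposed cohort will look safer. The documents do not establish that. T counts on-study time only, under the same 3-year plan in both cohorts. Prior use enters the total duration of exposure in SAP 8.3 but not T, and no on-study exposure by cohort is given.

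**Large effects need large hazards.** At an assumed 50 per 100 PY, 75 patients over 3 years would give 58 events in 225 PY, or 25.8 (19.6 to 33.3), which excludes 50. But that hazard means 1 − exp(−1.5) = 78% of those at risk develop one single PT within 3 years. Nothing in the documents supports this.

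**Other outputs exist.** These are the percentage of patients with an event, AESIs by onset interval, and shift tables for HbA1c, glucose and gallbladder findings. No hypothesis is tested. This lowers the stakes, but none of these outputs has an at-risk person-time denominator.

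**A first-event rate is no cure for a changing hazard.** With an assumed 40 per 100 PY for 6 months and 5 afterwards, it gives 23.5 at 1 year and 11.7 at 3 years (ratio 2.01), against a ratio of 2.18 for the SAP rate. This stands and shapes the fix.

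**Conclusion.** The point holds for persistent, once-recorded terms. For these the SAP rate understates onset and varies with follow-up, so it only partly does what SAP 8.4.1 asks of it. Under a constant hazard and one record per case, the 3-year shortfall runs from about 3% at a hazard of 2 per 100 PY to 42% at 40. For rare terms it is negligible, and with 100 to 200 patients it will often lie inside the confidence interval. The cohort ratio is distorted if on-study time differs or if prior users already have the condition. At equal hazards it is undistorted if neither applies.

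A reader might also infer that the SAP departs from Protocol 6.3, which says "Incidence rates by person-time of exposure and incidence rates by person-time of observation with their corresponding 95% confidence interval will be reported". On this point the documents do not support that. The protocol defines neither a first-event numerator nor a rule for ending person-time, so events over exposure time is not shown to breach it. The rate by person-time of observation is a separate matter.

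This is a cheap and worthwhile improvement. It does not show that the planned rate is invalid.

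**What to change.** In SAP 6.2.4 and 8.4.1, beside the occurrence rate, add an exposure-adjusted incidence rate for each displayed PT and each AESI category, overall and by cohort:

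- **Numerator:** patients with at least one treatment-emergent event.
- **Denominator:** the sum of t, with each patient's t ended at the onset of the first such event.
- **Limits:** the same Garwood formula.
- **Persistent PTs:** list them in advance. For these, show new onset among patients without the condition at Day 1, and report worsening of a pre-existing condition separately so that it is not lost.
- **Use:** interpret cohort differences in persistent events from this rate, read with the AESI onset-interval table because it still assumes a constant hazard. Keep the occurrence rate for recurrent events.

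While editing SAP 8.4.1, correct its pointer to Section 5.4, which does not exist; the method is in 6.2.4.

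Cost: SAP wording, one derived variable and one extra column per rate table. Event dates, medical history and dosing dates are already collected, so no new data are needed.

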#### **8.4.2 Laboratory evaluation**

All laboratory values will be converted into SI units.

Laboratory data will be classified (by biostatistics/SAS programming) into CTC grades according to the NCI Common Terminology Criteria for Adverse Events (CTCAE) v3.0. A severity grade of 0 will be assigned when the value is within normal limits. In the unlikely case when a local laboratory normal range overlaps into the higher (i.e. non-zero) CTC grade, the laboratory value will still be taken as within normal limits and assigned a CTC grade of zero.

For some laboratory tests, CTC grades are defined in two directions (low and high, e.g. for potassium: hypokalemia and hyperkalemia). The two directions will be analyzed separately.

The following summaries will be produced for the laboratory data (by laboratory parameter and direction of abnormality, as applicable):

- Shift tables using CTC grades to compare baseline to the worst post-baseline value
- Shift tables using CTC grades to compare the last post-baseline grade on treatment to the worst grade during the 90 days after permanent discontinuation of pasireotide s.c., in patients who discontinued pasireotide s.c. prematurely.
- For laboratory parameters where CTC grades are not defined, shift tables to the minimum and maximum post-baseline value using the low/normal/high classifications based on laboratory reference ranges.

Patients with laboratory values outside the laboratory reference range will be listed and flagged to show the corresponding CTC grades and the classifications relative to the laboratory reference ranges. In addition, laboratory values of patients with laboratory abnormalities of CTC grade 3 or 4 will be presented in separate listings.

HbA1c values will be classified into categories <5.7%, >=5.7% - <6.5% >=6.5% - 8% and >=8%, and categories cross-tabulated in shift tables (baseline versus worst post-baseline category).

---

Study Code: CSOM230B2410

A similar analysis will be performed for fasting glucose, classified into categories <100 mg/dL, >=100-<126 mg/dL, >=126 mg/dL (baseline versus worst post-baseline category).

The analyses of glucose will only include patients who were fasting at the time of blood sampling.

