3.5.2.6 Glucose metabolism

Alterations in blood glucose levels have been frequently reported in healthy volunteers and patients treated with pasireotide. Hyperglycaemia and, less frequently, hypoglycaemia, were observed in subjects participating in clinical studies with pasireotide s.c.

The degree of hyperglycaemia appeared to be higher in patients with pre-diabetic conditions or established diabetes mellitus. During the pivotal study, HbA1c levels increased significantly and stabilized but did not return to the baseline values. Less cases of discontinuation and lower reporting rate of severe AEs due to hyperglycaemia have been reported in patients treated with the dose of $600\mu\text{g}$ b.i.d.

The development of hyperglycaemia appears to be related to decreases in secretion of insulin (particularly in the post-dose period) and of incretin hormones (i.e. glucagon-like peptide-1 [GLP-1] and glucose-dependent insulinotropic polypeptide [GIP]).

Glycaemic status (fasting plasma glucose/haemoglobin A_{1c} [FPG/HbA_{1c}]) should be assessed prior to starting treatment with pasireotide s.c. FPG/HbA_{1c} monitoring during treatment should follow established guidelines. In addition, monitoring of FPG 4 weeks and HbA_{1c} 3 months after the end of the treatment is recommended. Self-monitoring of blood glucose and/or FPG assessments should be done every week for the first two to three months and periodically thereafter, as clinically appropriate.

If hyperglycemia develops in a patient being treated with pasireotide s.c., the initiation or adjustment of antidiabetic treatment is recommended, following the established treatment guidelines for the management of hyperglycemia. In the majority of patients who developed hyperglycaemia, the condition appeared to be manageable with appropriate antidiabetic therapy. If uncontrolled hyperglycaemia persists despite appropriate medical management, the dose of pasireotide s.c. should be reduced or pasireotide s.c. treatment discontinued.

Cushing's disease patients with poor glycaemic control (as defined by HbA_{1c} values $>8\%$ while receiving antidiabetic therapy) may be at higher risk of developing severe hyperglycaemia and associated complications. In patients with poor glycemic control the diabetes management should be intensified prior to initiation and during pasireotide therapy.

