3.5.2.12 Concomitant medications including significant non-drug therapies

All concomitant medications and significant non-drug therapies (e.g., surgery, radiation) will be recorded in this study on an ongoing basis. This will also include any information on antidiabetic treatment.

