#### 4.2.5 Prior and concomitant therapy

Prior and concomitant medications and significant non-drug therapies will be listed and summarized by cohort in the safety set.

Medications will be classified as prior or concomitant based on the following rules and will be coded using the WHO Drug Reference List (WHO DRL) dictionary that employs the WHO Anatomical Therapeutic Chemical (WHO ATC) classification system:

- Prior medications are medications that started before the first dose of study drug regardless of whether the medication ended before or after the first dose of study drug.
- Concomitant medications are medications that started on or after the first dose of study drug, or started before the first dose of study drug, and continued after the first dose of study drug.

The number and percentage of patients with prior and concomitant medications will be presented separately by ATC class and preferred term according to the WHO DRL dictionary.

---

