#### *8.2.1.4 Absolute and percentage change from baseline in clinical signs and symptoms*

For each time window, the absolute and percentage change from baseline in clinical signs and symptoms (blood pressure, body weight, body mass index, waist circumference) will be summarized with descriptive statistics. Distribution-free 95% CIs will be given for the median changes.

In addition, the absolute and percentage change from the last assessment while on pasireotide s.c. to the last value during the 90-days follow-up period will be summarized in a similar manner.

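### The HbA1c and fasting glucose shift tables take no account of antidiabetic treatment, so glycaemic worsening can be understated; the top two HbA1c bands also overlap at 8.0%

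*SAP*

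**What the plan says.** **Shift tables.** SAP 8.4.2: "HbA1c values will be classified into categories <5.7%, >=5.7% - <6.5% >=6.5% - 8% and >=8%, and categories cross-tabulated in shift tables". The comparison is "baseline versus worst post-baseline category". Fasting glucose is handled in the same way, with non-overlapping limits: "classified into categories <100 mg/dL, >=100-<126 mg/dL, >=126 mg/dL (baseline versus worst post-baseline category". Nothing in the section splits, flags or adjusts either table for antidiabetic treatment.

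**Treatment expected and recorded.** Protocol 3.5.2.6 says that if hyperglycaemia develops, "the initiation or adjustment of antidiabetic treatment is recommended". It also advises intensified diabetes management, before and during pasireotide, for patients with poor control. Protocol 3.5.2.12, on recording concomitant medication, adds: "This will also include any information on antidiabetic treatment".

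**Medication table.** SAP 4.2.5 tabulates prior and concomitant drugs by ATC class and preferred term. Concomitant drugs are those started on or after the first dose, "or started before the first dose of study drug, and continued after the first dose of study drug".

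**Blood pressure and lipids.** SAP 8.2.1.4 says that "the absolute and percentage change from baseline in clinical signs and symptoms (blood pressure, body weight, body mass index, waist circumference) will be summarized", and SAP 8.2.1.2 treats lipids in the same way. The mixed model in SAP 6.2.3 contains time window and baseline value only.

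**The concern.** Protocol section 1 gives long-term hyperglycaemia as a question that the pivotal trial could not address and as a reason for this study. Protocol 3.2 repeats it as an important safety evaluation. A drug that raises glucose, in a setting where raised glucose is treated, produces two signals: higher values, and more treatment. A shift table of values alone shows only the first, and the second reduces the first. A patient whose HbA1c stays in band because insulin was added appears in the same cell as a patient whose glucose metabolism did not change.

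The band overlap is a smaller matter. A programmer cannot apply the rule as printed to a value of 8.0%.

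**Working it through.** The plan states no figure on this point, so there is none to reproduce.

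**1. Which planned outputs use co-medication?**

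| Output | Uses antidiabetic or other co-medication? |
|---|---|
| HbA1c and fasting glucose shifts (SAP 8.4.2) | No |
| Blood pressure and lipid changes (SAP 8.2.1.4, 8.2.1.2) | No |
| Mixed model (SAP 6.2.3) | No |
| Monotherapy/combination groups (SAP 8.2.1, 8.3) | Cushing's disease therapy only |
| Sensitivity analyses (SAP 8.2.1) | No; they concern missing data |

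**2. Can new starts be read from the medication table?** Not from the table alone. The concomitant category pools new drugs with continued ones. Partial dates add to this. Under SAP 5.2, a drug is dated one day before treatment start if its start year is missing. The same applies if it started in the treatment-start year with the month missing, or in the treatment-start month with the day missing. Under SAP 5.1, an adverse event with the month missing in the treatment-start year is placed one day after the reference date. So a hyperglycaemia event and the drug given for it, both dated only to that year, fall on opposite sides of treatment start. For cohort 2, SAP 6.1.2 sets treatment start before study entry, so this reference date is not the first on-study dose.

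**3. Does the worst-value rule close the gap?** Only if a high value is recorded before treatment acts. Protocol Table 3-1 suggests HbA1c every 3 months, with weekly self-monitoring and/or fasting glucose for the first two to three months. Treatment can therefore begin before the first post-baseline HbA1c. The SAP does not say that home readings enter the fasting glucose table.

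**4. Effect on one patient** (assumed: rise 1.2 points, treatment effect 0.8 points, no higher value recorded first).
- Baseline 5.6%: 5.6 + 1.2 − 0.8 = 6.0, a shift of one band. Untreated, 5.6 + 1.2 = 6.8, a shift of two bands. Worsening is shown, but reduced.
- Baseline 5.7%: 5.7 + 1.2 − 0.8 = 6.1, no shift. Untreated, 5.7 + 1.2 = 6.9, a shift of one band. Worsening is not shown.

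**5. Effect on the share with HbA1c ≥8%** (all inputs assumed: untreated mean m, SD 1.2, fraction treated s, effect e acting fully on the value used).

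Share = (1 − s)·[1 − Φ((8 − m)/1.2)] + s·[1 − Φ((8 − m + e)/1.2)]

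Example with m = 7.0, s = 0.3, e = 1.0: 0.7 × 0.202 + 0.3 × 0.048 = 0.156, against 0.202 untreated.

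| m | Untreated | s = 0.3 to 0.6, e = 0.5 to 1.5 |
|---|---|---|
| 6.5% | 10.6% | 8.8% down to 4.6% |
| 7.0% | 20.2% | 17.3% down to 9.2% |
| 7.5% | 33.8% | 29.8% down to 16.4% |

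The reductions are smaller where the worst value precedes treatment. They are larger if treatment goes mainly to patients with high values, which the formula ignores. The table is an illustration, not an estimate for this study.

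**6. Band overlap.** Tested against the printed limits, 5.6, 5.7, 6.4, 6.5, 7.9 and 8.1% each fall in one band, and 8.0% falls in two. The share recorded as 8.0% to one decimal is Φ((8.05 − m)/SD) − Φ((7.95 − m)/SD). For an assumed mean of 6.0 to 7.5% and SD of 1.0 to 1.5, this is 0.5% to 3.5%, or about 1 to 7 of 200 patients.

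**7. Blood pressure.** With no pasireotide effect, a fraction s starting a drug worth e mmHg moves the mean by −s·e. Assumed s = 0.1 to 0.3 and e = 5 to 10 give −0.1 × 5 = −0.5 to −0.3 × 10 = −3.0 mmHg. The sign reverses if drugs are reduced or stopped.

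**The case against.** The strongest reply is that glycaemic harm is not judged by these tables alone. Under Protocol 3.5.2.1 an abnormal laboratory value that requires therapy is an adverse event, and the form records treatment introduced or adjusted. Such events enter the SAP 8.4.1 table of events needing additional therapy and the hyperglycaemia special-interest tables. The SAP 9.2 list for that category includes increased insulin requirement and insulin-requiring type 2 diabetes. If suspected to be related, they also count in the primary endpoint. The shift tables keep the worst category, and the medication listings show dates as collected. The study is exploratory and tests no hypothesis.

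Most of this stands, and it rules out a stronger reading. A reader might infer that glycaemic harm is hidden, or that improvements due to co-treatment are credited to pasireotide. The documents do not support either. The adverse event route captures much of the treated hyperglycaemia, and the SAP makes no causal attribution. For blood pressure and lipids, even the direction of any distortion is open. Protocol 3.5.2.7 foresees dose adjustment of beta blockers and calcium channel blockers, and co-medication may fall as well as rise.

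What the reply leaves open is narrower. No planned table relates HbA1c or fasting glucose to antidiabetic treatment. The special-interest table by event type has no column for additional therapy. Treatment intensified in advance, as Protocol 3.5.2.6 advises for poor control, need not be tied to a new event. Finding new starts in listings by hand is not a planned analysis.

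**Conclusion.** The point holds in limited form. As planned, the HbA1c and fasting glucose shift tables cannot separate patients whose values are held down by new or intensified treatment from those whose glycaemia did not change. They can therefore understate worsening on a question the study was set up to answer. The size cannot be computed, because the documents give no HbA1c distribution and no rate of antidiabetic use for this study; the ranges above rest wholly on assumed inputs.

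The 8.0% overlap is certain as printed but minor. It is probably a drafting slip, and it hides no harm. It does need reconciling with Protocol 3.5.2.6, which places poor control strictly above 8% and describes those patients as ones who, "while receiving antidiabetic therapy) may be at higher risk of developing severe hyperglycaemia". That is a risk description, not an analysis cut-point, so it does not settle which band 8.0% belongs to.

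For blood pressure and lipids, the documents support only a suggestion for clearer presentation.

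**What to change.** 1. **Shift tables.** Keep the planned HbA1c and fasting glucose tables. Repeat them by antidiabetic use at the first on-study dose (yes/no) and by new or intensified antidiabetic treatment on study (yes/no), within cohort. Add the number and percentage of patients with a higher category or new or intensified treatment. The split by on-study treatment is descriptive, since treated patients are selected for high values; the combined count is the better summary.
2. **Rules to state.** Define intensification. If dose changes turn out not to be recorded, limit it to a newly added drug and say so. For this analysis, name the first on-study dose as the reference date in both cohorts. State how partial medication dates are classified, with a category for timing unknown.
3. **Bands.** Make the top two HbA1c bands mutually exclusive, either by ending the third below 8% or by starting the fourth above 8%, and state how the choice relates to Protocol 3.5.2.6.
4. **Optional.** Beside the all-values tables, show blood pressure and lipid changes by relevant co-medication started or increased, unchanged, or reduced or stopped. Do not set aside values after a drug is started: that removes mainly patients whose values were high or rising.

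The cost is SAP wording, a few extra tables from medication data already collected, and a coding rule for intensification. With 100 to 200 patients split by cohort and treatment, some strata will be small, so counts should accompany every percentage.
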